Study Duration	8 months (Screening, 9 weeks of treatment visits with a 3-week break, and 6 months of phone/survey follow-up visits)		
Study Center(s)Center for Neuromodulation in Depression and Stress University of Pennsylvania School of Medicine Department of Psychiatry			
Objectives	We aim to compare the efficacy of rTMS treatment to two sub-regions of the Dorsolateral Prefrontal Cortex (DLPFC). We will examine the standard positioning of TMS used in clinical settings compared with TMS using MRI to guide the precise location of stimulation. We hypothesize that fMRI-guided TMS will produce greater benefit to patients with MDD/PTSD than the standard targeting method for TMS.		
Number of Subjects	N=80; n=40		
Main Inclusion and Exclusion Criteria	18-60; inclusive; no TMS contraindications; no medication use that substantially reduces seizure threshold or interferes with fMRI recordings; PTSD diagnosis or trauma induced MDD (SCID interview) and elevated depression (PHQ \ge 10).		
Investigational Product (drug, biologic, device, etc.)	MagVenture devices for rTMS administration include: -MagPro X100* magnetic stimulator -Cool-B65 Butterfly Coil		
Duration of administration (if applicable)	2 sets of 10 consecutive weekdays (at minimum 4 sessions per week with a total of 10 overall sessions per set)		
Reference therapy	N/A		
Statistical Methodology	Clinical outcome will be evaluated on symptom scales in a TMS target x Time ANOVA. Similarly, rate of change (slope) x TMS Target will indicate how rapidly each treatment improves symptoms.		

Safety Evaluations	TMS protocols will be administered by specially-trained staff from the Center or Neuromodulation in Depression and Stress the University of Pennsylvania Department of Psychiatry. All TMS staff will be trained by the PI ([name].) and the Center Director ([name].).		
Data and Safety Monitoring Plan	The PI will be responsible for monitoring the data quality and the ongoing safety of subjects.		

CONFIDENTIAL

BACKGROUND AND STUDY RATIONALE

Introduction

This study will be conducted in full accordance all applicable University of Pennsylvania Research Policies and Procedures and all applicable Federal and state laws and regulations including [as applicable include the following regulations as they apply 45 CFR 46, 21 CFR Parts 50, 54, 56, 312, and 812 and Good Clinical Practice: Consolidated Guidelines approved by the International Conference on Harmonisation (ICH). *Note: Only include ICH compliance if the study will actually comply with these requirements.*] *All episodes of noncompliance will be documented.*

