1.3 Dose Rationale

Several prior studies have safely utilized TMS outside of its FDA-approved protocol, even in substantially larger doses. For instance, in prior studies subjects have received the FDA-approved 3000 rTMS pulses, but done bilaterally instead of unilaterally (6000 total stimulations) every weekday over 4-6 weeks (see Bakker et al., 2015). Similarly, subjects have received 3600 rTMS pulses every weekday over 10 days (see Chistyakov et al., 2015), or 3000 rTMS pulses every weekday over 6 weeks (see O'Reardon et al., 2007). Another study applied the FDA-approved protocol in more than a double-dose, with 6800 stimulations to 1 site every weekday over 7 weeks average participation (Hadley et al., 2013). The present study utilizes many fewer stimulations than these recent/established protocols, with each visit including a maximum of 3700 pulses (including motor threshold determination).

2 Study Objectives

We aim to establish the clinical efficacy of TMS stimulation using targets defined by resting connectivity in patients. We hypothesize that MRI-defined TMS will yield greater reductions in symptoms and greater improvements in quality of life among patients. In addition, we hypothesize that greater resting state connectivity will predict greater reductions in symptoms following TMS.

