3.2 Study Endpoints

3.2.1 Primary Study Endpoints

The primary endpoint will be clinical improvement due to TMS at either of the two target regions. The study will focus on a target region of the fMRI-guided target and the standard DLPFC target, which is an FDA-approved rTMS treatment site. TMS-induced changes in brain activity are likely different for these two stimulation sites, despite their proximity. The aim of this study is to establish if using targets defined by resting connectivity in patients can be more effective at treating MDD/PTSD compared with standard targets.

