6.7 Safety Evaluations

Only individuals trained by the Principle Investigator ([name].) and Center Director ([name].) will dispense TMS. The licensed physician ([name] or a suitable medically trained stand-in) will closely supervise any medical instability in patients and will specifically be responsible for training and overseeing syncope and seizure management which are not expected given our screening process but are the two primary health risks with TMS treatment.

[name], a board certified physician, will review all questionable screens for MRI and TMS safety and will be physically present (or a reasonable medically trained stand-in) for every TMS session conducted on any participant who indicates greater than minimal risk for experiencing syncope or a seizure in response to TMS.

Only research personnel will have keys and access to the TMS devices.

7 Statistical Plan

All recruitment will be conducted through the University of Pennsylvania, the Veterans Administration Medical Center, and surrounding community to find 80 patients with PTSD or trauma induced MDD and depressive symptoms. It is anticipated that a large portion of individuals will screen fail, withdrawal from participation or have unusable data. Therefore, 80 individuals will be consented/enrolled in this study, to ensure that there are 40 patients who complete the full protocol with usable data. This sample should provide us with adequate data to compare treatment sites relative to one another, since all patients will receive the standard targeting for TMS and also fMRI-guided TMS.

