7.3 Sample Size and Power Determination

Using an effect size (Hedge's g) calculated from published work doing theta burst stimulation treatment for MDD to a nearby brain area (dorso-medial prefrontal cortex) in a sample of 87 patients and yielding an effect size of 1.225 (% improvement, Hamilton Depression scale), a priori power analysis (Power 0.80, p-

value 0.05) indicates that we will need at least 6 patients to generate a significant change in symptoms which is well below our planned enrollment.

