7.4 Statistical Methods

The primary analysis will be a Site x Time ANOVA on the Hamilton Depression rating scale comparing pretreatment to symptoms immediately following each round of stimulation. This test will be augmented by a Site x Time ANOVA for pre-treatment compared with the 6 month timepoint to explore the degree of maintenance of treatment benefits.

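### The Summary, the endpoint sections and 7.4 disagree on which scale and analysis carry the site comparison, and no multiplicity rule covers the alternatives

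*Combined protocol and SAP*

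**What the plan says.** - **Study Summary, Statistical Methodology:** "Clinical outcome will be evaluated on symptom scales in a TMS target x Time ANOVA. Similarly, rate of change (slope) x TMS Target". The scales are neither named nor counted. The slope analysis appears nowhere in Section 7.
- **7.4 Statistical Methods:** "The primary analysis will be a Site x Time ANOVA", on the Hamilton scale, from pre-treatment to immediately after each round. A second Site x Time ANOVA at 6 months is added to explore maintenance.
- **3.2.1 and 7.1:** the primary endpoint is clinical improvement, with no scale given. Section 3.2.1 adds the aim of showing that connectivity-defined targets "can be more effective at treating MDD/PTSD compared with standard targets".
- **Section 2, Study Objectives:** the hypothesis is that MRI-defined stimulation yields "greater reductions in symptoms and greater improvements in quality of life among patients".
- **1.1 Background:** names three measures for judging each site: MADRS for depression, the PCL for PTSD and WHOQOL for quality of life.
- **6.6 Efficacy Evaluations:** lists seven instruments: PHQ-9, PCL-5, MADRS, CSSRS, PANAS, WHOQOL-BREF and SHAPS. Hamilton is not among them.
- **7.2:** the only secondary endpoint is a connectivity correlation.

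No order of testing, alpha split or multiplicity rule is given anywhere.

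**The concern.** The places that should define the main comparison give three different answers: several scales by two methods (Summary), one scale by one method (7.4), and no scale at all (3.2.1, 7.1). The one scale that 7.4 protects is not on the list of efficacy instruments. Whoever runs the analysis will therefore have to choose a scale, and the text would permit that choice after the results are seen.

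At stake is the error rate behind a statement that guided targeting is better. The quality-of-life hypothesis, and any statement about PTSD symptoms, also have no named test that could support them.

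**Working it through.** **1. The plan's own figure.** Section 7.3 is the only place that gives an alpha. Its inputs are "yielding an effect size of 1.225 (% improvement, Hamilton Depression scale"), "a priori power analysis (Power 0.80") and a p-value of 0.05, giving at least 6 patients. For a paired change with a two-sided normal approximation:

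n = ((z0.975 + z0.80) / g)² = ((1.960 + 0.842) / 1.225)² = 5.23, rounded up to 6.

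The figure reproduces. It concerns a change in symptoms, not a difference between sites, so it says nothing about multiplicity. Section 7.4 states no alpha and no section states sidedness; two-sided 0.05 per test is assumed below.

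**2. Which tests could carry the claim.**
- 7.4 primary only: 1 test.
- Both 7.4 ANOVAs: 2 tests.
- The three domains in 1.1: 3 tests by ANOVA, 6 if slope is a separate test.
- All seven instruments in 6.6: 7 tests by ANOVA, 14 with slope. This is an upper bound that no section plans.

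**3. Formulas, assuming no true site difference.** For k independent tests, the chance of at least one significant result is 1 − 0.95^k in either direction, and 1 − 0.975^k in favour of the guided site. For example, 1 − 0.975^6 = 0.141 and 1 − 0.975^14 = 0.298. For correlated tests, multivariate normal draws were counted against ±1.96, with between-scale correlation 0.3 to 0.7 and correlation 0.5 to 0.9 between two tests of the same scale. The documents give no correlations, so these ranges are assumptions.

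**4. Results.**

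| Tests that may carry the claim | k | False guided-better: independent | correlated | Either direction: independent | correlated |
|---|---|---|---|---|---|
| 7.4 primary alone | 1 | 2.5% | n/a | 5% | n/a |
| Both 7.4 ANOVAs | 2 | 4.9% | 3.6–4.6% | 9.8% | 7–9% |
| Three domains, ANOVA only | 3 | 7.3% | 5–7% | 14.3% | 11–14% |
| Three domains, two methods | 6 | 14.1% | 8–12% | 26.5% | 15–24% |
| Seven scales, ANOVA only | 7 | 16.2% | 9–14% | 30.2% | 18–27% |
| Seven scales, two methods | 14 | 29.8% | 12–23% | 51.2% | 24–44% |

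**5. Whether slope is a separate test.** Section 6.6 schedules the instruments at baseline, after each two-week block and during the break. With one value before and one after a block, a slope within that block is the change score divided by time and adds nothing to the ANOVA. Section 6.2.2 mentions short assessments around each session but names no instrument. The ANOVA-only rows therefore apply to any scale not measured repeatedly within a block.

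**The case against.** The strongest reply is that 7.4 does name a single primary analysis, and that 7.3 and the interim rule in 7.4.3 use the same scale. A conclusion confined to that test has 5% two-sided error, or 2.5% for a false finding in favour of guided targeting. That is right in principle. It fails in practice because 6.6 does not list the Hamilton scale and 1.1 names MADRS as the depression measure.

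Other parts of the reply stand:
- A reader might infer that the Summary commits the trial to testing every scale twice, and so that a false guided-better claim has a 51% chance. The documents do not support this. The Summary does not say every scale; CSSRS and WHOQOL-BREF are not plainly symptom scales; no section plans 14 tests; and 51% counts both directions under independence.
- Nor does 7.4 confine itself to a single test, since it adds the 6-month ANOVA, although that one is labelled exploratory.
- The phrase MDD/PTSD may describe the population rather than a separate PTSD claim, and 7.4.2 refers to clinical symptoms in general. It would be too strong to say that PTSD symptoms will not be analysed. What can be said is that no test of PCL-5 is named.
- If PCL-5 and WHOQOL-BREF are never formally tested, they add no inflation; they then leave a gap between hypothesis and analysis. The text does not say which case applies.
- This is labelled Phase 1 with 40 evaluable patients, so calling the other scales exploratory would be a legitimate answer.

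**Conclusion.** The inconsistency holds and is worth correcting; the inflation is conditional. It arises only if success on any scale or method is allowed to stand as the finding, which nothing in the plan prevents.

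On that condition, and under the assumed correlations, the chance of a false guided-better result against a nominal 2.5% is about 8% to 12% for the three named domains by two methods (14% if independent). It is about 12% to 23% at the 14-test upper bound (30% if independent). In either direction, against a nominal 5%, the corresponding figures are about 15% to 24% (26%) and 24% to 44% (51%). If slope adds no separate test, the three-domain figure for a false guided-better result falls to about 5% to 7%.

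A far larger error rate as a settled feature of the plan is not shown. What is shown is that the single-test safeguard in 7.4 rests on a scale absent from the efficacy list, and that the quality-of-life hypothesis and the PTSD measure have no named test and no error control.

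**What to change.** 1. Make the Summary, 3.2.1, 6.6, 7.1 and 7.4 name the same single primary scale, one that is actually collected, and one site contrast with its time points, tested at two-sided 0.05. Bring the Hamilton references in 7.3 and 7.4.3 into line.
2. If that test is significant, test the same contrast on PCL-5 and then on WHOQOL-BREF, each at 0.05, stopping at the first non-significant result. Family error then stays at or below 5% (2.5% for a false guided-better result). Alternatively, label both exploratory and make no superiority claim on them.
3. Report the slope analyses, the 6-month ANOVA and the remaining scales as estimates with confidence intervals.

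If the chosen scale is already in 6.6, this is a change of wording with no added patients or visits. Keeping Hamilton would mean adding it to the assessments. The downside is that fewer scales can carry a formal claim, and under the fixed sequence a failed primary test ends formal testing of the other two.

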1.1 Background and Relevant Literature

The subgenual Anterior Cingulate Cortex (sgACC) has been well established as a brain area sensitive to negative mood inductions and implicated in neural abnormalities associated with affective and stress disorders. It is therefore one of the primary targets for deep brain stimulation (DBS) treatment of MDD using surgically implanted DBS devices. Recent posthoc imaging studies of patients who have undergone TMS treatment for depression suggest that treatment outcomes tended to be better when patients were by chance stimulated in an area of lateral prefrontal cortex that had high levels of functional connectivity with sqACC. Based on this finding and on our own interleaved TMS/fMRI probe data, we contend that targeting delivery of TMS to the brain surface non-invasively as indicated by sqACC resting functional connectivity may be especially effective in downregulating sqACC and thereby producing superior clinical outcomes. We have used TMS/fMRI to better understand causal communication among circuits typically examined with resting fMRI alone (Chen et al., 2013). Our recent work suggests that there are specific sites that, when stimulated, influence subcortical brain areas implicated in affective disorders such as the sgACC. Previously, we targeted TMS based on brain atlases mapped onto individual brain surfaces. This proposal will utilize more individualized targeting from participants own resting connectivity data to guide stimulation that we show is especially effective in influencing downstream brain areas of interest. We will focus on a target region that our data suggest is particularly effective at influencing the sqACC. As an alternative brain target, we will also test the efficacy of the dorsolateral prefrontal cortex as a target given its precedence as an FDA-approved stimulation site for remediating depressive symptoms. To increase generalizability to other disorders and to patients with comorbid anxiety and depression (the typical clinical profile), we will recruit patients who are diagnosed with PTSD or trauma induced MDD and who have elevated depression (PHQ). We will recruit them, scan them in the MRI to get anatomical and resting fMRI data to guide TMS, then will invite them to participate in two rounds of two-week TMS treatment to each site (order counterbalanced) with approximately one month between treatments. We will monitor depressive (MADRS), PTSD (PCL Checklist), and quality of life (WHOQOL) measures before, acutely after, and every month for 6 months following TMS treatments to evaluate the effectiveness of each site in mitigating symptoms or improving functioning. A typical, FDA-approved clinical application of TMS involves long trains of repetitive TMS applied for approximately 40 minutes, 5 days/week, over 2-6 weeks, for a total of 10-30 TMS visits. The present study utilizes the same FDA-approved devices (Magventure Cool-Coil B65, MagVenture X100 Stimulator) to administer treatment. We will be modifying the FDA-approved protocol to stimulate similarly to a well-replicated protocol, theta-burst stimulation (Huang et al., 2005). We have attached several additional examples of prior studies which have safely utilized TMS outside of its FDAapproved protocol, even in heightened doses. For instance, in prior studies subjects have received FDAapproved 3000 rTMS pulses, but done bilaterally instead of unilaterally (6000 total stimulations) every weekday over 4-6 weeks (see Bakker et al., 2015). Similarly, subjects have received 3600 rTMS pulses every weekday over 10 days (see Chistyakov et al., 2015), or 3000 rTMS pulses every weekday over 6 weeks (see O'Reardon et al., 2007). Another study applied the FDA-approved protocol in more than a double-dose, with 6800 stimulations to 1 site every weekday over 7 weeks average participation (Hadley et al., 2013). The present study utilizes fewer stimulations than the FDA-approved protocol, with each visit including a maximum of 3700 pulses. For additional information, please see Anderson et al., 2006 for demonstrations of the safety of repeated exposure to TMS. Likewise, please see Wagner et al., 2007 and Parkin et al., 2015 for reviews of the importance of TMS research and how our proposed studies fit in the present and growing body of literature.

1.2 Name and Description of the Investigational Product

This study will use investigational MagVenture devices for single-pulse and rTMS administration, including:

- MagPro X100* magnetic stimulator
- Cool-B65 Butterfly Coil

The MagPro X100* magnetic stimulator and Cool-B65 Butterfly Coil are FDA-approved for rTMS treatments of depression.

1.2.1 Clinical Data to Date

1.2.1.1 Clinical Studies in Adults

Repetitive TMS (rTMS) to the dorsolateral prefrontal cortex (DLPFC) is an FDA-approved treatment for major depressive disorder. A normal, FDA-approved clinical application of TMS involves long trains of repetitive TMS applied for approximately 40 minutes, 5 days/week, over 4-6 weeks, for a total of 20-30 TMS visits. Recent post-hoc imaging studies of patients who have undergone TMS treatment for depression suggest that treatment outcomes tended to be better when patients were by chance stimulated in an area of lateral prefrontal cortex that had high levels of functional connectivity with sgACC. Researchers have used TMS/fMRI to better understand causal communication among circuits typically examined with resting fMRI alone (Chen et al., 2013), suggesting there are specific sites that, when stimulated, influence subcortical brain areas implicated in affective disorders such as the sgACC.

This study will utilize individualized targeting from participants' own fMRI scans. We will focus on a target region that our preliminary data suggest is particularly effective at influencing the sgACC. As an alternative brain target, we will also test the efficacy of the standard dorsolateral prefrontal cortex (DLPFC) target.

1.3 Dose Rationale

Several prior studies have safely utilized TMS outside of its FDA-approved protocol, even in substantially larger doses. For instance, in prior studies subjects have received the FDA-approved 3000 rTMS pulses, but done bilaterally instead of unilaterally (6000 total stimulations) every weekday over 4-6 weeks (see Bakker et al., 2015). Similarly, subjects have received 3600 rTMS pulses every weekday over 10 days (see Chistyakov et al., 2015), or 3000 rTMS pulses every weekday over 6 weeks (see O'Reardon et al., 2007). Another study applied the FDA-approved protocol in more than a double-dose, with 6800 stimulations to 1 site every weekday over 7 weeks average participation (Hadley et al., 2013). The present study utilizes many fewer stimulations than these recent/established protocols, with each visit including a maximum of 3700 pulses (including motor threshold determination).

2 Study Objectives

We aim to establish the clinical efficacy of TMS stimulation using targets defined by resting connectivity in patients. We hypothesize that MRI-defined TMS will yield greater reductions in symptoms and greater improvements in quality of life among patients. In addition, we hypothesize that greater resting state connectivity will predict greater reductions in symptoms following TMS.

2.1 Primary Objective

• To assess and compare the clinical efficacy of rTMS treatments performed at the standard brain target versus an fMRI-guided brain target

2.2 Secondary Objectives (if applicable)

• To assess the correlation between resting-state connectivity prior to TMS and the degree of clinical change in response to TMS treatment targeting this circuit.

3 Investigational Plan

Visit #0:	Consenting / Screening procedures	
Visit #1/Baseline:	Baseline MRI Scan to determine TMS targets, clinical assessments, and	
	neuropsychological assessments	
Visit #2-11:	Targeting + TBS treatment and clinical assessments	
Break:	Subjects spend 3 weeks away from the lab,	
(Phone/Survey) Visits #	12 and 13: Clinical assessments	
Visit #14-23:	Targeting + TBS treatment and clinical assessments	
(Phone/Survey) Visit #2	4-29: Clinical assessments	
See Section 6. Study Procedures for specific assessments at each visit		

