3.1 General Design

TMS will be administered to either the fMRI-guided target or DLPFC in a randomized, single-blind design. 40 patients diagnosed with Post-Traumatic Stress Disorder (PTSD) or trauma induced Major Depressive Disorder (MDD) and symptoms of depression, as determined by meeting the DSM criteria for PTSD or MDD as a primary diagnosis and scoring ≥10 on the PHQ-9, will be recruited for this study. They will be otherwise healthy adults, aged 18-60, with PTSD or trauma induced MDD as primary diagnosis and without current diagnoses of significant, problematic substance use disorders or with present or past diagnoses of psychosis or bipolar illness. All subjects will receive active TMS, so there is no placebo or sham condition. However, the patients will be blinded as to whether their site of stimulation is based on the clinical standardized targeting method or our novel fMRI-guided targeting method. TMS is administered to one of these two sites over a two-week period, and then TMS will be administered to the other site over a subsequent two-week period following a three week wash out period. All subjects will receive TMS to both sites as a part of the study, but the order is randomized and counterbalanced. All participants will be recruited through the community via study advertisements and through the University of Pennsylvania and the VA. Subjects can express interest by contacting the study staff; in most cases, this will serve as the primary method for acquiring contact information. Physician referrals and the use of the Penn Data Analytics Center will also be incorporated as recruitment methods. Section 4.3 further elucidates all recruitment methods. Prior to any study visits, all subjects will be screened in a telephone interview with a trained member of the study staff or via a self-report screening survey. The first study session will consist of a consenting and extended screening visit. The information collected in this initial visit will determine if the subject meets all inclusion criteria. We will also demonstrate TMS to ensure the subject is comfortable with all study procedures. At the second study session, participants will undergo an MRI procedure for 60 minutes. This will be used to generate the TMS targets for the study. Subjects will then return every weekday (5 days per week, minimum of 4 days per week) over two weeks to receive the TMS treatment (10 sessions). These visits will last approximately 60 minutes each. The daily administration of TMS is a necessary component of the study, as it is consistent with the standard operating procedure for FDAapproved clinical TMS. During the 2 weeks of TMS treatment, subjects will undergo the many of the same clinical assessments used during the screening and baseline visits, in order to examine changes in symptoms. Subjects will then spend 3 weeks away from the study team; during the break, there will be two phone/survey visits used as a safety assessment. After this break, subjects will then return every weekday (5 days per week, minimum of 4 days per week) over two weeks to receive the TMS treatment (10 sessions) to the other site examined in the study. Upon completion of the study, scheduled phone and survey visits will take place every 4 weeks (+/-7 days) over the subsequent 6-month period to monitor continued stability of clinical improvement and/or remaining clinical symptoms. Overall, this study consists of 1 consent/screening visit, 1 MRI scan, 20 total visits for TMS treatment, and 8 phone visits.

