7.2 Secondary Endpoints

The secondary endpoint of this study will be the correlation between resting-state connectivity prior to TMS and the degree of clinical change in response to TMS treatment targeting each circuit.

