9.2 Data Collection and Management

Staff will be trained on the protocol and inclusion/exclusion criteria. Other facilities will include various laboratory spaces specializing in advanced computing and analysis of neuroimaging and cognitive datasets.

Structural and functional scans will be obtained in each session on a clinically-approved 3 Tesla Siemens Prisma (Erlangen, Germany) scanner housed in the Center for Advanced Magnetic Resonance Imaging and Spectroscopy (CAMRIS), equipped with 40mT/m gradients and 200 mT/m/s slew-rates. RF transmission will use a quadrature body-coil, and reception will use a Siemens receive-only 64-channel head coil. The total time in the scanner will be approximately 60 minutes. All MRI imaging will be reviewed and approved by CAMRIS. Additional MRI resources, such as a mock scanner, may be accessed from the Center for Functional Neuroimaging (CfN).

Patients entering the study will be given a unique identifying code. This code will be used on all data obtained from scans or the medical record. Only one password protected document connecting the code

with the participant name will exist. This subject key will be maintained on the University of Pennsylvania's secured server (aka, PMACS); only the research coordination team will have access to this key and a record will be kept of all personnel who have been granted access. All collected data will be immediately coded and this coded information will be stored in secure cabinets inside locked rooms or in password protected, IRB compliant online databases, such as REDCap. All data will be deidentified and only qualified research personnel will be have access. Records will be kept electronically on password protected servers. Deidentified information may be shared with collaborating researchers within the University of Pennsylvania and at collaborating institutions. This information will be stripped of all personal health information (PHI) and other personal identifiers.

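### The secondary connectivity correlation has no term for treatment round, although each site's data would by default mix about 20 first-round and about 20 second-round patients

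*Combined protocol and SAP*

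**What the plan says.** Section 2.2 sets one secondary objective: "To assess the correlation between resting-state connectivity prior to TMS and the degree of clinical change in response to TMS treatment targeting this circuit". Section 7.2 makes it the secondary endpoint, with clinical change defined as "the degree of clinical change in response to TMS treatment targeting each circuit", which points to one correlation per site. Section 3.2.2 describes the secondary endpoint differently: it relates fMRI activity at baseline, not connectivity, to improvement across the whole study, not to the response at each site.

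On imaging, the visit list in section 3 places the scan at Visit 1 ("Baseline MRI Scan to determine TMS targets, clinical assessments, and"), and section 3.1 counts "1 MRI scan, 20 total visits for TMS treatment". The procedures table in section 6 marks MRI at baseline only. Sections 6.2.1 and 9.2 contain a sentence that reads otherwise ("Structural and functional scans will be obtained in each session on a clinically-approved 3 Tesla Siemens Prisma"), which fits the rest only if it means each scanning session.

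On treatment, every patient receives both sites and "the order is randomized and counterbalanced" (3.1). Section 6.2.3 puts round 1 in weeks 1 and 2 and round 2 in weeks 6 and 7.

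On analysis, section 7.4 names Site x Time ANOVAs for the primary comparison and its six-month extension. It gives no method for the correlation and no term for round, period or order.

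**The concern.** For any one site, half the patients receive it as their first TMS course and half as their second. Average change may differ between a first and a second course for ordinary reasons: symptoms may already have fallen, scores may regress to the mean, or benefit from the first site may persist. A simple correlation across all completers counts that difference as unexplained scatter around the connectivity relation. Because order is randomised, round should be unrelated to Visit 1 connectivity on average. The main harm is therefore a smaller correlation and a less sensitive test, not a systematic false signal.

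This is the trial's only secondary endpoint. With about 40 completers, avoidable noise matters. Without a stated method, the choice among a pooled, a round-adjusted and a first-round-only analysis could also be made after the data are seen.

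**Working it through.** **Inputs from the documents.** One MRI at Visit 1 (3, 3.1, 6); ten sessions over two weeks per round and a three-week washout (3.1); rounds in weeks 1-2 and 6-7 (6.2.3); 40 evaluable patients (4.5); counterbalanced order (3.1).

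**Timing.** From the start of round 1 to the start of round 2 is 2 + 3 = 5 weeks, with 10 sessions in between. This is a minimum gap from scan to second-round treatment, because the interval from scan to round 1 adds to it.

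**Mixing.** 40 / 2 = about 20 first-round and 20 second-round patients in each site's correlation.

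**The plan's own power figure.** Section 7.3 gives at least 6 patients for a symptom change with g = 1.225, power 0.80 and alpha 0.05. A paired normal calculation, two-sided, gives (1.960 + 0.842)² / 1.225² = 5.23, rounded up to 6, so the figure reproduces. It does not bear on the correlation, for which no power is stated.

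**Effect of omitting round.** Let ρ be the correlation within a round and d the difference in mean change between rounds, in within-round SD units. With equal halves, the round difference adds d²/4 to the variance of change, so

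pooled r = ρ / √(1 + d²/4).

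Approximate power at two-sided 0.05 is Φ(atanh(r)·√(n − 3) − 1.96). With a round term, the partial correlation stays at ρ and √(n − 3) becomes √(n − 4). Both ρ = 0.50 and d are assumptions; the documents give neither.

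| d (SD) | pooled r | power, no round term | power, round term |
|---|---|---|---|
| 0 | 0.500 | 92% | 91% |
| 0.5 | 0.485 | 90% | 91% |
| 0.8 | 0.464 | 86% | 91% |
| 1.0 | 0.447 | 83% | 91% |

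Worked row for d = 0.8: √(1 + 0.64/4) = 1.077; 0.50 / 1.077 = 0.464; atanh = 0.503; 0.503 × √37 − 1.96 = 1.10; Φ = 0.86. With the term: 0.549 × √36 − 1.96 = 1.34; Φ = 0.91.

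**Simulation** (6,000 trials per setting, 20 patients per round, ρ = 0.50) agrees: with d = 0.8, about 87% without and 92% with the term; with d = 0, 92.8% without and 92.2% with it.

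**What the round term does not repair.** Suppose instead that the link itself is weaker in round 2, again an assumption, and that mean change does not differ. At 80% of its round-1 strength, power is 85.1% without and 84.2% with the term; at 50%, it is 68.3% and 66.9%. The term recovers a mean shift, not a weakened slope.

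**Can the data separate the two?** In the settings with a weaker round-2 link, a connectivity x round test has about 6-13% power. A slope from first-round patients alone (about 20) has about 64% power. Neither can explain a null result.

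**The case against.** The strongest objection is that the documents never state a pooled analysis. They name an endpoint, section 7.2 refers to each circuit, and section 7.4 is silent. That is correct: pooling over rounds is inferred as the default. Separating by site does not avoid it, since each site's data still come half from each round. Under the whole-study wording of 3.2.2, each patient would contribute a single change and the mixing would not arise in this form. That is a reason to reconcile the three sections.

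A second objection is that a baseline predictor is legitimate: connectivity before any TMS is a sensible moderator for both rounds. This stands, and nothing here calls for a second scan.

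A reader might go further and infer that second-round connectivity is out of date, that ten sessions at a neighbouring site have altered the circuit, and that pooling therefore dilutes a link that holds in freshly scanned patients. The documents do not support this. The statement in 1.1 that connectivity-guided targeting "may be especially effective in downregulating sqACC" concerns the effect of stimulation on the sgACC; it does not say that resting connectivity stays changed after a three-week washout. Section 3.2.1 expects the two sites to change brain activity differently and says nothing about persistence. Nor are first-round patients guaranteed a recent scan: no scan-to-treatment window is set, and section 12.3 allows an MRI from another study to be reused without an age limit.

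**Conclusion.** The point holds as a gap in specification with a nearly free improvement. The single scan, the counterbalanced order and the two rounds are documented; the missing round term follows from section 7.4's silence on this endpoint. At an assumed r of 0.50, adding round gains about 5 points of power if mean change differs by an assumed 0.8 SD (about 87% to 92%). It gains less for smaller differences and costs under one point if there is none. The true size cannot be derived from the documents.

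The point does not extend to attenuation by scan age or intervening stimulation. That is an assumption, a round term would not repair it, and the trial is too small to test it.

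**What to change.** In section 7.2, replace the simple correlation with a regression for each site: that round's clinical change on Visit 1 connectivity plus round (1 or 2), using all completers, with the connectivity slope pooled over rounds as the main result. State which score serves as the start of each round. Word 2.2 and 3.2.2 to match, so that all three sections name the same predictor (connectivity or activity) and the same outcome (change per site or over the whole study). Reconcile the each-session scanning wording in 6.2.1 and 9.2 with the single scan in 3.1.

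Slopes by round may be reported with confidence intervals, labelled descriptive, with a statement that they cannot show why a null result occurred.

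The cost is a few sentences and one degree of freedom per site. No further scan, visit or patient is needed.
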